#### **9.5.3.1.2 Documentation of Adverse Events**

AEs that occur during Screening and prior to dosing on Day 1 will be considered pre-treatment AEs. The TEAE reporting period begins with administration of the first dose of trial drug on Day 1 and continues until 3 weeks after the last dose of trial drug. The Follow-up AE reporting period begins 3 weeks after the last dose of trial drug through completion of the Follow-up Period. All pre-treatment AEs, TEAEs and AEs during the Follow-up Period must be recorded in the source documents and on the patient's eCRF.

If the Investigator observes an SAE after trial completion that he/she believes was possibly caused by trial drug, the Investigator will report this SAE using the procedures described in Section 9.5.3.1.5.

Detailed information regarding all SAEs must also be recorded on the Serious Adverse Event Reporting Form. Whenever possible, the Investigator should group together into a single term the signs and symptoms that constitute a single diagnosis. For example, cough, rhinitis and sneezing might be grouped together as "upper respiratory infection" if the Investigator is confident of the diagnosis. For diagnoses of infusion-associated events or anaphylaxis, signs and symptoms will be captured separately in the eCRF.

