#### 9.5.6.2.5 Week 24/End-of-Treatment 1/First Infusion of Open-label Treatment Period

Week 24 is the final visit of the double-masked Treatment Period. Trial drug is not administered for responders and non-responders who elect not to receive open-label TEPEZZA. For proptosis non-responders who elect to receive open-label TEPEZZA, the infusion will be performed at Week 24 (first of 8 infusions); all Week 24 procedures except AF and concomitant medication monitoring, post-infusion PK sample collection and 24-hour post-dose phone/email contact must be completed prior to TEPEZZA infusion.

- Perform efficacy assessments (proptosis, **CCI** [REDACTED] and GO-QoL questionnaire). The **CCI** will not need to be performed on the same day as other Week 24 assessments as long as it is performed within the visit window and prior to the first open-label infusion (proptosis non-responders who elect to receive open-label TEPEZZA).
- Perform CAS.
- Perform treatment response assessment, including whether the patient is a proptosis responder or non-responder, and enter data in EDC.

- Obtain blood samples for hematology and fasting chemistry (including thyroid and HbA1c) analysis.
- Collect urine sample for a pregnancy test for females of childbearing potential.
- Perform visual acuity assessment.
- Measure weight.
- Record vital signs (prior to and at the end of the infusion for non-responders who elect to receive open-label TEPEZZA). Additional vital sign monitoring may be performed in the event of infusion-associated AEs (see Section 9.5.3.4 for details).
- Collect blood samples for immunogenicity and **CCI** (NOTE: Collection should be prior to dose for non-responders who elect to receive open-label TEPEZZA.) Collect a single blood sample for PK analyses (proptosis responders and proptosis non-responders who elect not to receive open-label TEPEZZA). NOTE: **CCI**

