## 10 SOURCE DOCUMENTATION AND INVESTIGATOR FILES

The Investigator must maintain adequate and accurate records to document fully the conduct of the trial and to ensure that trial data can be subsequently verified. These documents should be classified in 2 separate categories: (1) Investigator trial file and (2) patient clinical source documents that corroborate data collected in the eCRFs. Patient clinical source documents include, as applicable, original hospital/clinic patient records; physicians' and nurses' notes; appointment book; original laboratory, electrocardiogram, electroencephalogram, radiology, pathology and special assessment reports; dispensing records; signed ICFs; consultant letters; and patient screening and enrollment logs.

In order to comply with regulatory requirements, it is the policy of the Sponsor that, at a minimum, the following be documented in source documents at the site:

- Medical history/physical condition and diagnosis of the patient before involvement in the trial sufficient to verify that the patient meets protocol entry criteria.
- Trial number, assigned patient number and verification that written informed consent(s) was(were) obtained (each recorded in dated and signed progress notes).
- Progress notes or equivalent source documentation for each patient visit and contact (each dated and signed).
- Records of each trial visit including each trial assessment and the identity of the staff member performing the assessment.
- Trial drug dispensing and return.
- Review by the Investigator or qualified personnel of laboratory test results.
- AEs (start and stop date, description, relationship to trial drug, action taken and resolution).
- Investigator or sub-investigator's signed assessment of each AE.
- Concomitant medications (start and stop dates, reason for use).
- Condition of patient upon completion of, or PW from, the trial.

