10.1 Adverse Events

Adverse events will be coded using MedDRA version 24.0. AEs that occur during Screening and prior to dosing on Day 1 will be considered pre-treatment AEs. TEAEs for the double-masked treatment period is defined as AEs with onset date on or after the first dose of study drug during the double-masked treatment period prior to receiving the first dose of TEPEZZA during open-label treatment period for patients who entered open-label treatment period, or through 3 weeks (21 days) after the last dose of study drug during the double-masked treatment period for patients who did not enter open-label treatment period. TEAEs for open-label treatment period defined as AEs with onset date on or after first dose of TEPEZZA during the open-label treatment period through 3 weeks (21 days) after last dose of TEPEZZA during the open-label treatment period. All analyses for TEAEs will be split to TEAEs reported during the double-masked treatment period and open-label treatment period separately. The follow-up AE reporting period begins 3 weeks (21 days) after the last dose of study drug through completion of the follow-up period.

An overall summary of all TEAEs including the number and percentage of patients experiencing at least one occurrence of a TEAE, serious TEAEs, treatment-related TEAEs, treatment-related serious TEAEs, TEAEs resulting in study drug discontinuation, TEAEs of special interest, TEAEs leading to death along with the summary of National Cancer Institute Common Terminology Criteria for Adverse Events (NCI-CTCAE) grade 3 or higher will be provided.

Additionally, AEs and SAEs reported during the follow-up period after each treatment period will be presented by SOC and PT separately.

All AEs, AEs with CTCAE Grade 3 or higher, SAEs, AEs leading to discontinuation of study drug, AE of special interest, and deaths will be presented in separate by-subject listings.

Signs and symptoms associated with Infusion reaction and anaphylaxis will be recorded and included in a by-subject listing.

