19. CCI

20. Not collected for patients who prematurely discontinue from the double-masked Treatment Period.
21. For those patients who have consented, photographs of the patient's eyes will be taken prior to the first infusion and at Week 24 (all patients) and Week 48 (non-responders who elect to receive open-label TEPEZZA).
22. For non-responders who choose to receive open-label treatment, TEPEZZA infusion will be performed at Week 24 (first of 8 infusions). All Week 24 assessments except AE and concomitant medication monitoring, post-infusion PK sample collection and 24-hour post-dose phone/email contact must be completed prior to TEPEZZA infusion.
23. Phone (or email) contact by research staff focusing on safety and tolerability aspects will be made the day after infusion for the first and second infusions during the double-masked Treatment Period and during the open-label Treatment Period, and thereafter as deemed appropriate. In addition, patients who experience an infusion-associated event after any subsequent infusion will also be contacted by phone (or email) by research staff the day after the infusion, and thereafter as deemed appropriate.

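### The SAP's two TEAE definitions are not mutually exclusive on the first open-label infusion day, so adverse events found before that infusion can leave the double-masked table or be counted in both periods

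*SAP*

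**What the plan says.** SAP 10.1 splits all TEAE summaries by treatment period.

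- **Open-label period:** "TEAEs for open-label treatment period defined as AEs with onset date on or after first dose of TEPEZZA during the open-label treatment period", continuing to 21 days after the last open-label dose.
- **Double-masked period, patients who enter open label:** from the first dose of study drug, with the end set at "prior to receiving the first dose of TEPEZZA during open-label treatment period for patients who entered open-label treatment period".
- **Double-masked period, all other patients:** "through 3 weeks (21 days) after the last dose of study drug during the double-masked treatment period".

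Protocol 9.5.6.2.5 makes Week 24 both the last double-masked visit and, for entrants, the visit of the first open-label infusion. Apart from AE and concomitant-medication monitoring, the post-infusion PK sample and the next-day contact, the Week 24 procedures "must be completed prior to TEPEZZA infusion". Footnote 22 of the schedule in SAP 15.1 says the same. Those procedures include hematology, chemistry, thyroid tests, HbA1c, visual acuity and pre-infusion vital signs.

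For the first dose of the trial, both documents separate what precedes the infusion: "AEs that occur during Screening and prior to dosing on Day 1 will be considered pre-treatment AEs". There is no parallel sentence for the first open-label dose.

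**The concern.** The design places a full set of safety assessments and the first open-label infusion on one visit, normally one date. A rule that compares only dates cannot tell a finding made before the infusion from one that arose after it. The wording resolves the tie towards open label.

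Two things are at stake. First, Week 24 is the last look at the masked exposure, and an event first dated there can leave the randomized TEAE comparison. Second, for former placebo patients a finding made before any TEPEZZA would be reported as emergent on TEPEZZA. That conflicts with SAP 5.4.2, where the last value before the first TEPEZZA dose is the TEPEZZA Baseline. The same pre-infusion measurement would then serve as baseline and as the source of an on-treatment event.

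Open-label entry is offered only to proptosis non-responders, a post-randomization outcome. The share of patients exposed to the problem can therefore differ between arms.

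**Working it through.** The plan states no figure on this point, so there is none to reproduce. The check applies the SAP 10.1 rules to onset days around Week 24.

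**Inputs**
- Study day = assessment date − Day 1 + 1 (SAP 5.4.1), so week *w* falls on day 7*w* + 1. SAP Table 1 gives the Week 24 target as Day 169, which agrees.
- Last double-masked dose: Week 21 (SAP 3.1).
- First open-label dose: Week 24.
- Planned arms: 38 TEPEZZA, 19 placebo (SAP 5.1).

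**Days, with on-schedule dosing**
- Week 21: 7 × 21 + 1 = Day 148.
- Week 24: 7 × 24 + 1 = Day 169.
- End of the 21-day window for non-entrants: 148 + 21 = Day 169, inclusive.

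**Classification by onset date**

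| Onset day | Enters open label | Does not enter |
|---|---|---|
| 168 | Double-masked | Double-masked |
| 169 | Open-label | Double-masked |
| 170 | Open-label | Follow-up |

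The Day 170 row is as it should be: the entrant has received open-label drug. Day 169 is the anomaly. Two patients with the same finding, at the same pre-infusion assessment and after the same masked exposure, go into different tables.

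**Two readings for an entrant's pre-infusion finding dated Day 169**
1. *Both definitions by date.* The onset date is not before the first open-label dose date, so the event is not double-masked. It is on that date, so it is open-label. The double-masked table loses it.
2. *Double-masked definition by sequence, open-label definition by date as worded.* The finding preceded the infusion, so it is double-masked. Its onset date equals the dose date, so it is also open-label. It is counted in both periods.

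**Size of one reclassified patient**
- TEPEZZA arm: 1/38 = 2.6 percentage points.
- Placebo arm: 1/19 = 5.3 percentage points.

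This is the change in a given row of the TEAE table when the moved event is that patient's only event in the row.

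**The case against.** The strongest reply is that the double-masked wording already describes a sequence, which a pre-infusion finding satisfies, and that the open-label wording refers to the first dose rather than its date. If the AE form records onset time, a programmer could allocate events correctly. This stands in part: the AE form is not available, so whether time or a flag is collected cannot be settled. Protocol section 10 lists AE start and stop date, without time, but only as a minimum for source documents. Even so, the sequence reading does not cure the open-label definition, which is keyed to onset date. It replaces a loss with an overlap.

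It is also fair that Week 24 data are not lost. SAP 10.2 to 10.4 summarize laboratory values (including glucose grades), vital signs and visual acuity by visit and arm from the measurements themselves. All AEs are listed by patient, open-label results are shown by original arm (SAP 4.3), and no safety hypothesis is tested. New visual acuity findings attributed to TED are generally not reported as AEs, so that assessment adds few cases.

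Two stronger readings are tempting and are not supported:
- *Day 1 has the same fault.* It does not. Both documents expressly class pre-dose Day 1 events as pre-treatment.
- *A fixed share of events is moved, because Week 24 is one of four scheduled post-baseline chemistry tests and one of two for HbA1c.* The documents give no entry rates and no basis for equal detection at each visit. Protocol 9.5.3.1.1.5 also calls for HbA1c every 6 weeks in patients with known diabetes, so the one-in-two count fails for the group most likely to have hyperglycemia.

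**Conclusion.** The concern holds for a defined set: events in open-label entrants whose onset is dated to a pre-infusion Week 24 assessment, when the infusion is given that day. Symptoms reported at Week 24 with an earlier onset date stay double-masked. For the affected events the SAP gives either a loss from the double-masked TEAE table or a double count, and it does not say which.

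The total effect cannot be estimated from the documents. Its direction by arm is also not established. If more placebo than TEPEZZA patients are non-responders and enter, which is an assumption, the placebo column would be affected more often. The comparison with non-entrants assumes on-schedule dosing; a non-entrant's Week 24 visit more than 21 days after the last dose would fall in the follow-up AE period.

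A reader might infer that Week 24 hyperglycemia disappears from the masked comparison. It does not, because the by-visit laboratory tables keep the values. The defect is confined to the TEAE and AESI tables. It is worth correcting because the arms are small and the design creates the boundary for every entrant.

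**What to change.** In SAP 10.1, make the two definitions mutually exclusive. An AE dated on the day of the first open-label infusion is a double-masked TEAE if a pre-infusion Week 24 assessment found it or if it began before the infusion started. It is an open-label TEAE only if onset is after the infusion start. For laboratory findings, the rule should follow the time of the sample, since central laboratory results may arrive after the visit.

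Infusion start and stop times are already recorded (Protocol 9.4.10), so the only further need is AE start time or a before/after-infusion flag for events on that date. The cost is one sentence or two in the SAP and, if not already collected, one extra AE field. Patients, dosing and visits are unaffected. It should be settled before the double-masked database lock, so that events are not allocated case by case after unmasking.

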10.1.1 Incidence of Adverse Events

The incidence of AEs will be reported by SOC and PT level for each treatment period. The patient will be counted only once in corresponding category if the patient experiences more than one event under the same SOC or PT level.

The total number of TEAEs and the number and percentage of patients with at least one TEAE for each SOC and PT will be presented by treatment group.

Incidence of TEAEs by SOC and PT by the following subgroups for each treatment period will be provided.

- Race (White, Black or African American, Asian, Other)
- Tobacco use status (Non-user, User)
- Age (<65 years, >=65 years)
- Sex (Male, Female)

For race, if the number of patients in any of the race groups is less than 5, we will pool “Black or African American”, “Asian”, “Other” into “Non-White”. For other variables, if the number of patients is less than 5 in any subgroup, then subgroup analysis will not be performed. For tobacco use status, tobacco uses of “Never” or “Former” will be grouped as tobacco “Non-users”, and tobacco uses of “Current” will be considered tobacco “Users” on the substance use eCRF.

10.1.2 Relationship of Adverse Events to Study Drug

The relationship between study treatment and AE will be captured on the eCRF. The AE records with missing relationship information will be summarized as related AEs.

Summary of all TEAEs and SAEs respectively will be presented by SOC, PT and relationship (Unrelated/Related) to study drug.

10.1.3 Severity of Adverse Event

The severity of AEs will be evaluated by the NCI-CTCAE (v4.03). the grade will be assessed by the investigator as mild (Grade 1), moderate (Grade 2), severe (Grade 3), life-threatening (Grade 4), or fatal (Grade 5).

For AE grade tables, the patient will be counted once with the highest-grade event if he/she experiences more than one event under given SOC or PT level.

A summary of CTCAE Grade 3 or higher TEAEs by SOC and PT will be presented by treatment group.

Summary of all TEAEs and SAEs respectively will be presented SOC, PT and maximum severity of AEs.

10.1.4 Serious Adverse Events

The SAE is defined as any event that results in death, is immediately life threatening, requires inpatient hospitalization or prolongation of existing hospitalization, results in persistent or significant disability/incapacity, or is a congenital anomaly/birth defect.

A summary of all SAEs by SOC and PT will be presented by treatment group.

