###### 9.5.3.1.1.2 Serious Adverse Event Definition

A treatment-emergent adverse event (TEAE), Baseline event, or suspected adverse reaction is considered serious if, in the view of either the Investigator or Sponsor, it results in any of the following outcomes:

- Death. This includes any death that occurs during the conduct of a clinical trial, including deaths that appear to be completely unrelated to the trial drug (e.g., due to car accident).
- Life-threatening adverse experience. An AE or suspected adverse reaction is considered life-threatening if, in the view of either the Investigator or the Sponsor, its occurrence places the patient at immediate risk of death. It does not include an AE or suspected adverse reaction that, had it occurred in a more severe form, might have caused death.

- Persistent or significant disability or incapacity.
- Inpatient hospitalization or prolongation of an existing hospitalization.
- Congenital anomaly or birth defect.
- Another medically important event that, according to appropriate medical judgment, may require medical or surgical intervention to prevent 1 of the outcomes listed above.

Surgical procedures or other therapeutic interventions themselves are not AEs, but the condition for which the surgery intervention is required is an AE and should be documented accordingly.

Elective surgeries that require hospitalization and treatment received at an emergency room or similar facility will not be considered as SAEs unless 1 of the definitions of an SAE listed above is met.

In addition, a hospitalization for planned procedures is not considered an AE unless the hospitalization becomes prolonged. An emergency room visit less than 24 hours in duration is not considered a hospitalization.

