#### 9.5.3.1.5 Reporting and Documenting Serious Adverse Events

All SAEs beginning with the time of signing of the ICF and continuing until 30 days after trial discharge must be reported. The following steps will be taken to report promptly and document accurately any SAE, whether or not it appears to be related to trial drug:

1. Report the SAE to the Sponsor by **entering the information in the eCRF within 24 hours** after becoming aware that a patient has experienced an SAE. If unable to access the eCRF, the event must be reported by submitting the completed SAE form by email to [[contact]](mailto:[contact]), or via fax **within 24 hours** after becoming aware that a patient has experienced an SAE (see [Appendix 17.1](#) for contact information).
2. Perform appropriate diagnostic tests and therapeutic measures, and submit all follow-up substantiating data, such as diagnostic test reports, hospital discharge summaries and autopsy report to the Sponsor's representative.
3. Respond in a timely manner to any queries from Sponsor regarding the SAE.
4. Conduct appropriate consultation and follow-up evaluation until the SAE is resolved, stabilized, or otherwise explained by the Investigator.
5. Review each SAE report and evaluate the relationship of the SAE to trial treatment. The Sponsor will determine whether the SAE is unexpected in nature.
6. The Investigator must report to the IRB all AEs or SAEs that meet the criteria for Unanticipated Problems Involving Risks to Human Subjects or Others.

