3.2.4 Safety and Tolerability Endpoints

1. The incidence of treatment-emergent adverse events (TEAEs,) serious adverse events (SAEs), TEAEs resulting in premature discontinuation of treatment and AESIs (infusion reactions, hyperglycemia, hearing impairment, new onset inflammatory bowel disease and exacerbation of inflammatory bowel disease).
2. The incidence of \geq Grade 3 TEAEs.
3. The change from Baseline to each scheduled visit in vital signs (blood pressure, heart rate, respiratory rate and temperature).
4. The results of best-corrected visual acuity.
5. The incidence of \geq Grade 3 fasting glucose values.
6. The change from Baseline to each scheduled visit in laboratory evaluations (hematology and chemistry [including thyroid panel and HbA1c]).

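### The SAP's definition of a serious adverse event omits the protocol's medically-important-event criterion, so SAE outputs could leave out reported SAEs if SAP 10.1.4 is applied literally

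*SAP*

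**What the plan says.** Protocol 9.5.3.1.1.2 says that an event "is considered serious if, in the view of either the Investigator or Sponsor, it results in any of the following outcomes" and lists six items. The first five are death, a life-threatening event, disability or incapacity, inpatient hospitalization or its prolongation, and congenital anomaly or birth defect. The sixth is "Another medically important event that, according to appropriate medical judgment, may require medical or surgical intervention to prevent 1 of the outcomes listed above". The same section adds that "An emergency room visit less than 24 hours in duration is not considered a hospitalization". Under protocol 9.5.3.1.5 the site reports an SAE to the sponsor by "entering the information in the eCRF within 24 hours" of becoming aware of it.

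SAP 10.1.4 opens with "The SAE is defined as any event that results in death, is immediately life threatening" and completes the list with "requires inpatient hospitalization or prolongation of existing hospitalization, results in persistent or significant disability/incapacity, or is a congenital anomaly/birth defect". The next statement in that section is "A summary of all SAEs by SOC and PT will be presented by treatment group". SAE incidence belongs to the first safety endpoint in SAP 3.2.4: "The incidence of treatment-emergent adverse events (TEAEs,) serious adverse events (SAEs), TEAEs resulting in premature discontinuation of treatment and AESIs".

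**The concern.** One component of a safety endpoint is defined in two ways. The SAP wording is a definition and its list is closed: it has no catch-all item and no reference to the protocol section. The omitted criterion is not redundant. Because the protocol does not count a short emergency room visit as a hospitalization, an event treated without admission that is neither immediately life-threatening nor disabling can be serious only as a medically important event.

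What is at stake is agreement between the analysis and the safety reporting. If 10.1.4 were programmed as written, an event reported as serious under the protocol could be missing from several outputs: the SAE table in 10.1.4, the serious and treatment-related serious TEAE rows of the overview, the follow-up SAE summary and the SAE listing in 10.1, and the SAE tables by relationship and by severity in 10.1.2 and 10.1.3. The study report would then disagree with the SAEs reported during the trial.

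**Working it through.** The plan states no figure on this point, so the check is a comparison of texts, followed by a scale calculation.

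**Step 1. Criteria side by side**

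| Criterion | Protocol 9.5.3.1.1.2 | SAP 10.1.4 |
|---|---|---|
| Death | yes | yes |
| Life-threatening | yes | yes |
| Hospitalization or prolongation | yes | yes |
| Disability or incapacity | yes | yes |
| Congenital anomaly or birth defect | yes | yes |
| Other medically important event | yes | **no** |

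The count is six against five.

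**Step 2. Is the difference explained elsewhere?** SAP section 13 lists the changes from the protocol's planned analysis, and a narrower SAE definition is not among them. SAP section 1 says the SAP rests on protocol version 4.0 (Amendment 3.0, administrative change 1), whereas the current protocol is version 5.0. The version 5.0 summary of changes lists no change to the SAE definition, so nothing in the documents attributes the gap to the older version. The SAP sentence is complete and not redacted.

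**Step 3. Does the SAP name a source for seriousness?** For neighbouring attributes it does. Relationship comes from the eCRF (10.1.2), grade from the investigator (10.1.3), discontinuation from the AE page of the eCRF (10.1.5) and infusion reactions from the AE form (10.1.6). For seriousness it names no source and gives a definition instead.

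**Step 4. Does the SAP filter recorded SAEs?** No such step is written. Sites enter SAEs under the protocol, and the SAP tabulates all SAEs. Events would be lost only if the five-item list were used to derive or re-check seriousness.

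**Step 5. Scale.** The inputs are the planned arm sizes, 38 on TEPEZZA and 19 on placebo (protocol 9.6.7, SAP 5.1), assuming that every randomized patient is dosed and so enters the safety set. If one patient's only SAE met the sixth criterion alone and was dropped, incidence in that patient's arm would fall by 1/n:

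- TEPEZZA: 1/38 = 2.6 percentage points
- Placebo: 1/19 = 5.3 percentage points

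The documents give no expected SAE rate and no share of SAEs resting on the sixth criterion, so the number of such patients cannot be estimated.

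**The case against.** The strongest reply is that 10.1.4 is an incomplete background paraphrase above a table of collected SAEs. Seriousness is decided by the investigator or sponsor under the protocol and recorded by the site. Where the SAP wants a programmed rule it writes one: date windows for TEAEs (10.1), MedDRA searches for most AESIs (10.1.6), imputation of missing intensity and relationship (5.5.3). It writes none for seriousness. On that reading nothing is lost, and section 13 is silent because no change was intended.

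This stands as far as the consequence goes. A reader might infer that the SAE endpoint will necessarily omit every event that is serious only as medically important. The documents do not support that, because it needs a filtering step that the SAP does not contain.

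A reader might also infer that the under-count would fall mainly on TEPEZZA, since that is where drug reactions are expected. That too is unsupported. It needs the same filtering step, plus an excess on TEPEZZA of events serious under the sixth criterion alone, for which the documents give no figure. Several obvious candidates could meet retained criteria: protocol 9.5.3.1.1.5 calls diabetic ketoacidosis and hyperosmolar state life-threatening, anaphylaxis can be so as well, and permanent hearing loss can be a disability. The same section reports that hearing events and muscle spasms in earlier trials were non-serious and that infusion-related events had not been anaphylactic.

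It is also true that AESI tables, Grade 3 or higher tables, discontinuation tables and listings of all AEs would still show many such events, whatever their seriousness classification.

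The reply does not remove the contradiction. The SAP presents the sentence as its definition, and the reference to all SAEs follows it directly. With no other source named, a programmer could reasonably take the five items as the rule.

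**Conclusion.** The discrepancy is real and undeclared: the SAP defines part of its first safety endpoint by five of the protocol's six criteria. Applied literally, SAP 10.1.4 could make the SAE tables, listings and serious-TEAE overview rows disagree with the SAEs reported under the protocol. The documents do not establish that it would.

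The size cannot be computed. The per-patient figures of 2.6 and 5.3 points show only how much one reclassified patient matters in arms of 38 and 19. They assume that all randomized patients are dosed and that the patient had no other SAE. No direction of bias between the arms can be claimed.

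SAP section 10 plans no hypothesis tests on safety data, so no significance level, power or efficacy conclusion is affected. This is a wording error in an operative definition that should be corrected before the tables are programmed.

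**What to change.** In SAP 10.1.4, replace the definition with the six criteria of protocol 9.5.3.1.1.2, or simply cite that section. Add that every SAE output takes seriousness from the eCRF seriousness record, covering the tables, the listings and the serious-TEAE rows of the overview.

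The cost is one or two sentences in the SAP. Data collection, the protocol, the sample size and the planned tests do not change. Because this brings the SAP back to the protocol, section 13 needs no entry. If the sponsor does intend the narrower definition, section 13 should declare it with a reason.
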